12.1 Primary analysis: MDS UPDRS

A two-tailed independent samples t-test will be used to compare change in MDS UPDRS motor score (post-stimulation at final "on" visit" - baseline) in the treatment versus placebo group. A priori alpha level=.05. Cohen's d will be used to examine effect of stimulation on motor scores.

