At the **screening visit** (visit SC) we will obtain informed consent, review inclusion and exclusion criteria, medical history, demographics. We will obtain a baseline MoCA exam, based on proposed exclusionary criteria. For those enrolled, medications used in the treatment of PD will be held constant throughout the study. Baseline blood draw in the amount of 3 teaspoons (<15ML) for biomarkers will be obtained by appropriately trained personnel. Urine pregnancy test will be administered to women of childbearing potential. We will randomize the patient to sham (n=15) versus active taVNS stimulation (n=15), and obtain baseline cognition battery (in normal *ON PD medication state*) at this time.

At **visit 1**, MDS UPDRS motor evaluation will be videotaped in the *OFF PD medication state* (defined as at least 12 hours without PD medication). Stimulation or sham will occur over 1 hour as defined below, and then repeat MDS UPDRS motor evaluation will be videotaped. A blinded rater will later score the modified (minus rigidity) MDS UPDRS on all videos at completion of the study.

Visits 2-4 are stimulation treatment visits in the *ON med state* with safety assessments, but no efficacy measures.

Visit 5 (study mid point) includes *OFF med* motor evaluation pre/post stimulation as at visit 1, in addition to the stimulation session.

Visit 6 is a taVNS treatment visits in the *ON med* state with additional behavioral saccade testing.

Visits 7-8 are stimulation treatment visits in the *ON med state* with safety assessments, but no efficacy measures.

Visit 9 is an *ON med* stimulation visit, and includes repeat cognition battery following the stimulation session.

Visit 10 (final day of stimulation) includes *OFF med* motor evaluation pre/post stimulation as at visit 1, in addition to the stimulation session. Repeat blood draw.

Visit 11 (Safety follow up visit) six to fourteen days after visit 10, we will check for any adverse events that might have occurred since the last stimulation session.

SCHEDULE OF ACTIVITIES

	Screening Baseline			Maintenance Phase					Follow up
	Visit SC Week 0-2 (-14d)	Visit 1 Stim day 1	Visit 2-4	Visit 5	Visit 6	Visit 7-8	Visit 9	Visit 10	+6-14 days
Written Informed Consent	x								
Eligibility Criteria	x								
MoCA	x								
Med/Neuro History	x								
Physical Exam	x								x
Blood Draw	x								
Cognitive Battery	x						x		
C-SSRS	x				x		x		
Pre-stim MDS UPDRS		x		x					x
stimulation thresholds		x							

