7.3 Review Medical History

The principal investigator or designated study physician must see the patient before randomization. The physician is responsible for fully assessing whether the patient has any of the conditions listed as contraindications, chiefly a history of myocardial infarction or

arrhythmia, bradycardia, epilepsy, metal implants above the shoulders, active respiratory disorder. The presence of any contraindicated condition or medication, which are itemized in the baseline eligibility, constitutes an exclusion criterion.

8. Stimulation Visits

At **visit 1**, MDS UPDRS motor evaluation will be videotaped in the *OFF PD medication state* (defined as at least 12 hours without PD medication).

Stimulation dosing will be assessed as above. Then taVNS or sham stimulation will occur over 1 hour. Acute pupillometry testing will be done. Then repeat MDS UPDRS motor evaluation will be videotaped (assessment of acute taVNS effect). A blinded rater will later score the modified (minus rigidity) MDS UPDRS on all videos at completion of the study.

Visits 2-4 are routine stimulation treatment visits in the *ON med state* with safety assessments, but no efficacy measures.

Visit 5 (study mid point) includes *OFF med* motor evaluation pre/post stimulation as at visit 1, in addition to the stimulation session. (used as mid point motor evaluation).

Visit 6 is a stimulation treatment visits in the *ON med* state with additional behavioral saccade testing. (used as mid point cognition marker free of practice effects, not administered at visit 5, as visit 5 is an *OFF med* visit)

Visits 7-8 are taVNS treatment visits in the *ON med state* with safety assessments, but no efficacy measures.

Visit 9 is an *ON med* stimulation visit, and includes repeat cognition battery following the stimulation session. (The cognition battery is not administered at visit 10, as visit 10 is an *OFF med* day.)

Visit 10 (final day of stimulation) includes *OFF med* motor evaluation pre/post stimulation as at visit 1, in addition to the stimulation session. Repeat blood draw.

9. Specimen Collection

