Consented patient participants will be assigned a random *4-digit study ID number and blood serum samples will be drawn by appropriately trained staff. There will be two blood draws per patient; one baseline and one at the conclusion of the study. Blood samples will be delivered to [name] lab as soon as possible, following all standard procedures for safe transportation and storage. [name] personnel will be blinded to sample name, diagnosis, and all other personal identifiers.

A paper log containing names and corresponding study IDs will be kept in a locked room and locked filing cabinet in the Movement Disorder Program Suite. This room will not be accessed by patients, and is separate from the room where patient evaluations are performed.

10. Follow up visit

Visit 11 (Safety follow up visit) 6-14 days after visit 10, we will check for any adverse events that might have occurred since the last stimulation session, just as we have with every visit.

11. Outcomes Assessments

11.1 Primary outcome: Clinically meaningful treatment difference of the MDS - UPDRS motor section

Videotaped, modified UPDRS evaluations have been established as a reliable research method with very high correlation to full UPDRS assessments.¹⁴ The UPDRS is modified due to the fact rigidity is not assessed by a rater watching a videotaped examination.

The six motor examinations will be compared for both acute as well as cumulative effects of stimulation:

- 1) Visit 1 pre-stimulation comparison to visit 1 post stimulation: acute effect
- 2) Visit 5 pre-stimulation comparison to visit 5 post stimulation: acute effect
- 3) Final Visit 10 pre-stimulation comparison to Visit 10 post stimulation: acute effect
- 4) Visit 5 pre stimulation comparison to Visit 10 pre-stimulation: subacute effect
- 5) Visit 1 pre-stimulation comparison to final Visit 10 pre-stimulation: subacute effect
- 6) Visit 1 pre-stimulation comparison to final Visit 10 post-stimulation: subacute effect

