12.3 Power Analysis

This study has been designed to provide adequate power to address the primary hypothesis and corresponding analysis. Significant placebo effects have been found in many clinical trials of pharmacologic interventions for motor symptoms in PD. However, a recent meta-analysis found no significant placebo effect associated with sham rTMS on short or long-term changes in UPDRS in PD.¹⁶ Given that there are no prior studies from which to estimate treatment or placebo effects associated with taVNS in PD, we powered our study to detect a clinically meaningful change of -3.25 on the UPDRS,¹⁷ with treatment taVNS. assumed a small and statistically non-significant change of -1 on the UPDRS with sham taVNS, and a standard deviation (pooled) of 2.0. At 80% power and alpha=.05, using a two-tailed t-test for difference in means, the total sample size required is 26 (13 per group). Prior studies in this clinic have found attrition to be about 10% for short-duration clinical trials. Accordingly, a sample of 35 participants will be enrolled.

13. Data, safety, and quality assurance monitoring

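### Optional improvement to section 12.1: the unadjusted t-test on motor change is valid, but pre-specifying ANCOVA on the visit 1 pre-stimulation score would remove dependence on chance baseline imbalance at little cost

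*Combined protocol and SAP*

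**What the plan says.** Section 12.1 gives one primary analysis: "A two-tailed independent samples t-test will be used to compare change in MDS UPDRS motor score". The change is defined as "post-stimulation at final 'on' visit' - baseline", at alpha .05, with Cohen's d as effect size. No covariate is named. The only adjustment anywhere in section 12 is the demographic correction of the cognitive scores in 12.2.

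A baseline motor score is nevertheless planned. Section 11.1 lists six comparisons, the last being "Visit 1 pre-stimulation comparison to final Visit 10 post-stimulation: subacute effect". Sections 3 and 8 place the visit 1 examination before stimulation and say of it: "MDS UPDRS motor evaluation will be videotaped in the *OFF PD medication state". Section 8 adds: "Visit 10 (final day of stimulation) includes *OFF med* motor evaluation pre/post stimulation as at visit 1". On scoring, it says: "A blinded rater will later score the modified (minus rigidity) MDS UPDRS on all videos at completion of the study".

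Section 12.3 assumes changes of -3.25 (taVNS) and -1 (sham) "and a standard deviation (pooled) of 2.0". It concludes, "using a two-tailed t-test for difference in means, the total sample size required is 26 (13 per group"), and sets enrolment at 35 after citing attrition of about 10%.

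**The concern.** Subtracting baseline is full correction with a slope of 1. When baseline and final scores have equal spread and correlate at rho below 1, the right slope is rho, so the change score over-corrects. Let D be the chance difference in baseline means, active minus sham. The expected change difference is then the true effect minus (1 - rho)D. An arm that starts worse is favoured through regression to the mean.

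Randomization takes place at the screening visit, before the visit 1 motor examination, and section 5 describes only an expected 1:1 ratio. As described, the allocation does not balance the arms on this score, so any adjustment has to come from the analysis. With 13 to 16 patients per arm, a reader of a positive result could fairly ask whether the worse-starting arm simply regressed. What is at stake is that question and possibly some efficiency. Type I error is not at stake.

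**Working it through.** **Inputs.** From 12.3: difference 3.25 - 1 = 2.25; SD 2.0, read as the SD of change because the assumed effects are changes; two-sided alpha .05; 13 per arm. From 12.3 and section 5: 35 enrolled, 1:1, attrition about 10%, so 35 × 0.9 = 31.5, or about 16 per arm. Assumed, because the documents give no value: rho from 0.5 to 0.98, and equal baseline and final SDs.

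**1. The plan's own figure.** n per arm = 2 × 2.0² × (1.960 + 0.842)² / 2.25² = 12.4, rounded up to 13. This reproduces the stated 26. By the noncentral t, 13 per arm gives 78.6% power (noncentrality 2.25 / (2.0 × √(2/13)) = 2.87, 24 df) and 16 per arm gives 86.8% (3.18, 30 df).

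**2. Residual variance under ANCOVA.** With equal spread s, the variance of change is 2s²(1 - rho) = 4, so s = 2 / √(2(1 - rho)). The ANCOVA residual SD is s√(1 - rho²), and its variance relative to that of change is (1 + rho)/2.

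**3. Power.** The ANCOVA figures use the noncentral t on N - 3 df, averaged over chance baseline imbalance.

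| rho | implied baseline SD | variance ratio | ANCOVA, 16 per arm (t-test 86.8%) | ANCOVA, 13 per arm (t-test 78.6%) |
|---|---|---|---|---|
| 0.5 | 2.0 | 0.75 | 93.7% | 87.3% |
| 0.7 | 2.6 | 0.85 | 90.6% | 83.0% |
| 0.8 | 3.2 | 0.90 | 89.0% | 80.9% |
| 0.9 | 4.5 | 0.95 | 87.3% | 78.7% |
| 0.98 | 10.0 | 0.99 | 85.9% | 77.1% |

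Sections 3 and 7.1 give 15 per arm. At that number the t-test has 84.5% power, against 92.0%, 88.5%, 86.7%, 84.9% and 83.4%.

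**4. Break-even.** The gain is nil at rho 0.926 for 16 per arm (baseline SD 5.2) and 0.908 for 13 per arm (baseline SD 4.7). Above that, ANCOVA loses slightly: 86.8 - 85.9 = 0.9 points at rho 0.98 with 16 per arm, and at most about 1.9 points with 13 per arm as rho approaches 1.

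**5. Unequal spread.** These thresholds move if the SDs differ. At 13 per arm with the SD of change held at 2.0, rho 0.7 and a final SD 1.2 times baseline give 78.1% (no gain). Rho 0.9 and a ratio of 0.9 give 84.7% (a clear gain).

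**6. Chance imbalance.** A one-standard-error baseline difference shifts the change-score estimate by (1 - rho) × s × √(2/n). At 16 per arm and rho 0.7 this is 0.3 × 2.58 × 0.354 = 0.27 points; at rho 0.9 it is 0.1 × 4.47 × 0.354 = 0.16. At 13 per arm and rho 0.7 it is 0.30 points: t-test power is then about 89.5% if the active arm starts worse and 67.5% if sham does, against 83.0% for ANCOVA either way. This is part of the variance already counted in step 3, not a further loss.

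**7. Validity.** In simulated null trials at 13 per arm, both tests rejected in 4.9% to 5.1% of trials. The change difference regressed on D had slope -0.50, -0.30, -0.20 and -0.10 at rho 0.5, 0.7, 0.8 and 0.9; the ANCOVA estimate had slope 0.00.

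**The case against.** The strongest reply is that nothing here is broken. The t-test is valid, it matches the test that 12.3 powers, and at the planned enrolment it exceeds its 80% target in a self-described pilot. That stands, and it is why the point is optional. A reader might infer that the missing covariate biases the trial or leaves it underpowered. The documents support neither: the test holds its alpha, and the imbalance effect averages out over randomizations.

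A reader might also infer that ANCOVA is bound to gain power, or that fixed cut-offs such as rho 0.7 and 0.91 settle the matter. They do not. Under the plan's SD of change and equal spread, rho 0.7 needs a baseline SD of only 2.6 points. Nothing in the documents supports so narrow a spread among Hoehn and Yahr 2-3 patients aged 40 to 82. If the baseline SD is above about 5.2, there is no average gain at 16 per arm. The 13-per-arm figures are also not the expected case: falling from 35 to 26 would be attrition of 9/35, about 26%.

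Finally, changing a primary analysis while the PI is unmasked (section 5) needs care. Motor examinations also serve as safety assessments (sections 6.3 and 14.5), and 13.1 lets the DSMB see partly unblinded outcome comparisons. These passages do not show that motor scores by arm exist before the videos are scored at study completion, so pre-specification remains feasible. The amendment should state explicitly that none has been seen.

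**Conclusion.** The point holds as an optional, low-cost improvement. Its firm benefit is that, under the usual linear model, the primary estimate no longer depends on which small arm happened to start worse. The average power gain is unknown. Under the assumptions in the table, at about 16 per arm it runs from +6.9 points at rho 0.5 (93.7 - 86.8) through +3.8 at 0.7 and +0.5 at 0.9 to -0.9 at 0.98. All of these figures rest on 2.0 being the SD of change, equal spread at the two examinations, and both scores being taken in the same medication state.

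**What to change.** Before any motor score is seen by arm, amend 12.1 so that the primary analysis is an ANCOVA. The outcome is the final post-stimulation modified motor score, treatment arm is the factor, and the visit 1 pre-stimulation modified motor score is the covariate. Use two-sided alpha .05 and report the adjusted difference with its 95% CI. Keep the change-score t-test and Cohen's d as supportive. Record that the amendment precedes scoring of the videos. In 12.3, state whether 2.0 is the SD of change.

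The cost is one degree of freedom, at most about 1.9 points of power at 13 per arm if rho is very high, and a written amendment to the IRB (14.2). No new data are needed.

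A separate matter must be settled in the same text: 12.1 places the endpoint at the final ON visit, while sections 3 and 8 describe the visit 10 motor examination as OFF medication. These passages must be reconciled, and baseline named explicitly, before either analysis can be run as written.

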12.2 Secondary analysis: Cognition and Serum markers

Measures of central tendency and distribution characteristics will be examined for all measures. Appropriate transformations and screening of outliers will be applied as indicated.

Generalized eta-squared¹⁵ will be calculated from repeated measures ANOVAs to examine cognitive change between groups over the 2 time points. For each time point, a composite score for cognition will be estimated by the average of demographically-corrected raw scores. The subjective measures of cognitive functioning will be analyzed in a similar manner. Cohen's d will be used to examine effect of stimulation on serum biomarkers.

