Specific Aim 1: To examine in a 2-week, randomized, sham controlled, double blind trial the effect of taVNS on motor symptoms in patients with mild to moderate motor symptoms of PD.

Hypothesis: taVNS will be superior to sham stimulation on its effects on the motor section of the Movement Disorder Society Unified Parkinson's Disease Rating Scale (MDS UPDRS; primary outcome measure).

Specific Aim 2: To examine in a 2-week, randomized, sham controlled, double blind trial the effect of taVNS on cognitive symptoms in PD.

Hypothesis: taVNS will be superior to sham stimulation on its effects on a composite score of the following cognitive assessment tools: DKEFS, Stroop, Digit symbol, Digit span forward and backwards, Fixation (control), Reflexive, and saccade inhibition tasks, CAARS, PROMIS (secondary outcome measure).

Specific Aim 3: To assess safety and tolerability of taVNS in PD.

Hypothesis: Treatment with taVNS will be as well tolerated as sham stimulation on the following parameters: acute monitoring of vital signs, MDS UPDRS motor evaluations and cognition testing to evaluate for worsening PD severity, adverse events or serious adverse events assessments, and the Columbia Suicide Severity Rating Scale (CSSRS). (tertiary outcome measure)

Specific Aim 4:(exploratory aim) To evaluate effects of taVNS versus sham stimulation on biomarkers relevant to VNS neurobiology.

Hypothesis: taVNS and not sham stimulation will lead to a decrease in serum inflammatory biomarkers (TNF-alpha, and IL-6), increase in serum BDNF, and increase in resting pupil diameter.

3. Design

Overview:

This pilot study of taVNS in PD intends to prove basic concepts of acute motor and cognition improvements with taVNS in PD patients. We will accomplish this by a two-week, single site, parallel, randomized, double blinded, sham-controlled pilot study of taVNS in 35 PD patients. There will be 1 screening visit, 10 stimulation visits, and 1 follow up visit.

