11.2 Secondary outcomes: Cognition and Biomarkers

To examine taVNS effect on cognition, a battery of behavioral and cognitive tasks relevant to PD will be assessed. We will utilize both objective and subjective measures. We will assess baseline, midpoint, and final cognitive function.

Cognitive battery:

- 1) DKEFS (Delis-Kaplan Executive Function System) verbal fluency and switching:
10 minutes
- 2) Stroop written test: 4 minutes (including start up and instructions)
- 3) Digit symbol computer based: 4 minutes (including start up and instructions)
- 4) Digit span forward and backwards: 3 minutes
- 5) Fixation (control), Reflexive, and saccade inhibition tasks: 5 minutes (including start up and instructions)

Additional subjective patient reported measures:

- 1) CAARS (Conners' Adult ADHD Rating Scales) (3 minutes)
- 2) PROMIS Sleep-Related Impairment (1 minute), PROMIS Applied Cognitive Abilities (1 minute), PROMIS Fatigue (1 minute)

To examine taVNS effect on serum markers associated with PD and neurobiology of VNS, measures of BDNF, TNF-alpha, and IL-6 will be obtained at baseline and after completion of final stimulation session. Laboratory samples will be assayed using ELISA.

To examine whether taVNS leads to the predicted pupillary resting state dilation, Eye tracking with computerized software will be used.

Pupillometry will involve a computer-based system in which an individual will receive stimulation while software records the movements and dilation of the pupil. The system used involves a setup in which infrared cameras are used to monitor the pupil in a luminance-controlled room. Participants will look at a computer screen and be instructed to maintain gaze within a specific area of the screen. IR cameras will track and monitor pupil diameter during stimulation.

11.3 **Tertiary outcome:** Safety and Tolerability

Safety and tolerability will be monitored for mean change, at each visit, from baseline to follow up. All stimulation visits include monitoring adverse events as well as vital signs. 3 visits include C=SSRS admin, 2 visits include cognition battery, 2 visits include additional physician physical examination. The follow up visit will be one additional visit 6-14 days following stimulation to specifically monitor for delayed adverse events, and will include a physical examination. Adverse events will be documented.

12. Statistical Analysis

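### Specific Aim 2 puts CAARS and PROMIS inside the cognitive composite and section 12.2 analyses self-report separately; 12.2's averaging rule also fixes no common metric or direction

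*Combined protocol and SAP*

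**What the plan says.** Specific Aim 2 (section 2) states the hypothesis that "taVNS will be superior to sham stimulation on its effects on a composite score of the following cognitive assessment tools". The list that follows names DKEFS, Stroop, Digit symbol and Digit span, and ends "Fixation (control), Reflexive, and saccade inhibition tasks, CAARS, PROMIS (secondary outcome measure". So CAARS and PROMIS belong to the composite being tested, and the aim labels that composite the secondary outcome measure.

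Section 11.2 numbers five items as the cognitive battery. It places CAARS and PROMIS under a different label, "Additional subjective patient reported measures", with three PROMIS scales: "PROMIS Sleep-Related Impairment (1 minute), PROMIS Applied Cognitive Abilities (1 minute), PROMIS Fatigue (1 minute". The notes under the Schedule of Activities make the same split.

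Section 12.2 says that generalized eta-squared "will be calculated from repeated measures ANOVAs to examine cognitive change between groups over the 2 time points". It defines the composite, formed separately at each assessment, in one clause: "a composite score for cognition will be estimated by the average of demographically-corrected raw scores". The next sentence reads "The subjective measures of cognitive functioning will be analyzed in a similar manner". The only wording about rescaling is general and follows a sentence on distributions: "Appropriate transformations and screening of outliers will be applied as indicated".

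**The concern.** Two analysts working from this text could test different outcomes for Aim 2. One would average five objective tests. The other would add self-report, as one PROMIS component or as three. No section says which definition governs. If the choice is left until the data are unblinded, it can be made with the results in view.

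The averaging rule is also incomplete. It speaks of raw scores and names no target scale, no norms, no weights and no direction. By their names, the Sleep-Related Impairment and Fatigue scales run opposite to Applied Cognitive Abilities. Averaging them without reversing signs would let a benefit on one cancel a benefit on another. The documents state no scoring direction for any scale, so this rests on the names alone.

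**Working it through.** The documents attach no figure to the composite, so there is nothing to reproduce. The conflict is established by the text, and the arithmetic only shows how much the choice could matter. Section 12.3 powers the primary hypothesis only and 12.2 states no alpha for cognition, so I compare effect sizes and not power.

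**Inputs.** From the documents: five objective items (11.2); seven tools in Aim 2 if PROMIS is counted once; nine measures if its three scales are counted separately. Assumed: a benefit of 0.5 SD of change on each improving measure, equal SDs, and a common correlation ρ between aligned changes of 0, 0.3 or 0.6. Then d is the mean effect of the averaged components divided by the SD of that average.

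**1. Membership, all scores aligned, only the five objective tests improve.** The summed effect is 5 × 0.5 = 2.5 in every case.

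- Five tests: d = 2.5/√(5 + 20ρ).
- Seven tools: PROMIS is the mean of three scales, with variance (1 + 2ρ)/3. Six single measures contribute 6, and 21 pairs contribute 42ρ. So d = 2.5/√(6 + (1 + 2ρ)/3 + 42ρ).
- Nine measures: d = 2.5/√(9 + 72ρ).

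| Composite | ρ = 0 | ρ = 0.3 | ρ = 0.6 |
|---|---|---|---|
| Five tests (12.2) | 1.12 | 0.75 | 0.61 |
| Seven tools (Aim 2, PROMIS as one) | 0.99 | 0.57 | 0.44 |
| Nine measures (Aim 2, PROMIS as three) | 0.83 | 0.45 | 0.35 |

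At ρ = 0.3 the denominators are √11 = 3.317, √19.133 = 4.374 and √30.6 = 5.532.

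If every measure improves equally, the summed effects are 2.5, 3.5 and 4.5. At ρ = 0.3 this gives 0.75, 0.80 and 0.81, so membership then matters little.

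**2. Direction, all measures improve, Sleep-Related Impairment and Fatigue left unreversed.**

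- Seven tools: the PROMIS mean has effect (0.5 − 0.5 − 0.5)/3 = −0.167, so the sum is 3 − 0.167 = 2.833. The variance is 6 + 30ρ + (3 − 2ρ)/9 − 4ρ, which is 14.067 at ρ = 0.3. So d = 2.833/3.751 = 0.755, against 0.80 aligned. At ρ = 0 it is 1.13 against 1.39, and at ρ = 0.6 it is 0.61 against 0.62.
- Nine measures: the sum is (7 − 2) × 0.5 = 2.5 and the variance is 9 + 16ρ. At ρ = 0.3, d = 2.5/√13.8 = 0.67, against 0.81 aligned. At ρ = 0 it is 0.83 against 1.50, and at ρ = 0.6 it is 0.58 against 0.62.

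**3. Scale alone, five tests, all aligned, ρ = 0.3.** Here d = 0.5 × ΣSD/√(0.7 × ΣSD² + 0.3 × (ΣSD)²). With assumed SDs of 10, 10, 10, 3 and 10, d = 21.5/√841 = 0.74. With the last SD set to 60, d = 46.5/√5331 = 0.64. Standardised scores give 0.75.

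**The case against.** The strongest reply is that 12.2 is the operative analysis text, and that it agrees with 11.2 and the schedule notes in keeping self-report apart. On that view one line in the aims is out of step, and the loss from direction needs Aim 2's membership combined with 12.2's averaging rule, a mixture that no section prescribes. This largely stands. It limits the direction argument and indicates which text to amend. It does not remove the conflict, because Aim 2 is where the hypothesis and the secondary outcome are stated.

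It can also be said that demographic correction implies normed scores on a shared scale. That is a fair reading, and it would largely remove the scale problem for normed tests. The text does not say so, and direction would still be unstated.

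A reader might infer more than the documents support:

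- **One test dominates the objective composite, or a benefit shows as harm.** This needs particular SDs and an unreversed score. The documents give neither, and no reversal within the objective battery is shown.
- **A drop from 1.50 to 0.50.** This needs nine uncorrelated measures and CAARS also keyed so that higher is worse, which no section states.
- **An unsigned effect size leaves a directional hypothesis untestable.** The direction can be read from the group means, so reporting a signed difference is a preference.
- **Fatigue and Sleep-Related Impairment have no analysis.** Section 11.2 lists both among the subjective measures for the cognition outcome, so the natural reading covers them.

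**Conclusion.** The concern holds as a conflict over membership, together with an incomplete averaging rule. The conflict follows from the text and needs no assumption. Its size is illustrative: with a benefit confined to the objective tests and ρ = 0.3, the composite effect is 0.75, 0.57 or 0.45 depending on the definition, and the gap nearly closes if self-report improves equally. The direction loss is conditional on averaging oppositely keyed self-report scales unaligned. It is then slight with seven tools and moderate with nine measures at ρ = 0.3. The effect of scale alone is modest in the cases tried.

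This is minor. It touches one secondary outcome of a pilot study and leaves the primary motor analysis and the sample size unchanged.

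**What to change.** Before unblinding:

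1. Amend Aim 2 to match 12.2: the composite is the objective battery, and CAARS and the three PROMIS scales are analysed separately.
2. In 12.2, list the scores that contribute to the composite. Replace the averaging of raw scores with an average of component scores on one metric, either z-scores on the pooled baseline mean and SD or one named normed scale, all oriented so that higher is better.
3. Apply the same sign alignment to any summary of the self-report scales.

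The repeated-measures ANOVA can stay. The cost is one line in Aim 2, a few lines in 12.2 and a few lines of code, with no new data.
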